**Data and Safety Monitoring**

Adverse side effects of the beeswax-pine resin mixture placed on the skin may include redness, rash, skin irritation, and infection. In the duration of the seven-day period, subjects will be provided a survey at the end of each day to assess their overall well-being and to provide them a space to express any concerns they may have. Any significant infection or irritation of the skin that causes serious concern for the subject will be evaluated by a licensed physician to evaluate whether they can continue in the study. Any signs of infection or other adverse side effects will result in the immediate cessation of the seven-day period for that subject.

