## Standard Research Summary

### Purpose of the Study:

The objective of the study is to determine whether the beeswax-pine resin mixture used as part of the LowCostomy appliance as a buffer can be safely applied to human skin. "Safe" is defined as no greater external skin irritation or injury compared to standard commercially available ostomy appliance products such as the Hollister Adapt Seal barrier ring, used in a similar manner to the beeswax-pine resin buffer as part of the LowCostomy appliance (3). The hypothesis to be tested is that the beeswax-pine resin mixture is safe for topical application to human skin.

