Photo documentation with the dedicated camera will occur on Day 1 at the initial screening visit as noted above, as well as Day 7. Photos will be collected by trained personnel in a private room without windows. A licensed physician will grade the blinded photos, indicating the appropriate level of skin irritation and rash by utilizing the Draize skin scoring system. Subjects will be given contact information to report any skin irritation or other adverse events during the 7-day trial period. Should a severe skin reaction occur, subjects will be directed to the licensed physician reviewer or a consult with a dermatologist. All subjects will record their experience through a RedCap survey which will include the 5D itch scale. After quantitative values have been assigned to each of the blinded photos, data visualizations will be created, and appropriate statistical analysis will be completed to evaluate for significant differences between each of the samples applied to subjects' skin.

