#### **Subject Recruitment and Compensation**

Potential participants will be recruited from the community. Advertising materials in the form of flyers that contain a QR code directing interested participants to the study's website will be placed around Duke's campus and clinical settings as well as broader public spaces. Additionally, Duke's ListServ email system will be utilized to recruit participants. Potential participants that express interest will be contacted by phone to further discuss study details, answer questions, review pertinent eligibility criteria, and preschedule study activities. Potential participants will not be contacted more than three times, including via letter, phone, email, and face-to-face interaction. If a participant states they would like to opt out, the study team will follow the Duke Recruitment and Engagement policy. Those who are

interested will be able to participate if they meet inclusion and exclusion criteria. A minimum of 50 subjects will be recruited. Incentive payment for subjects to participate in the study will be \$50.

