**Risk/Benefit Assessment:**

The main risk of the study is a reaction or skin irritation caused by the beeswax-pine resin mixture. This could include an allergic reaction, local skin irritation, redness, itchiness, or in severe cases blistering. Based on background research of existing beeswax-pine resin products, it has been hypothesized that a reaction is unlikely, but still possible. If a reaction occurs that is too uncomfortable to continue the study for the entire 7 days, the subject may stop early, and the reaction will be noted. The risks of the study are not being borne by the likely beneficiaries. The test subjects will likely not gain any health benefits from participating in the study; such subjects are not colostomy patients and hence not the target consumers of the LowCostomy appliance. Further, if an ostomy patient happens to participate in the study, he/she will likely return to the use of higher-priced medical-grade colostomy appliances without the use of the beeswax-pine resin mixture as the LowCostomy device will be marketed to populations in low-resource settings. The analysis expected to result from the tests is more valuable to the target low-income patients of Sub-Saharan Africa, who would be using this mixture on their skin. This is the main purpose of providing a monetary incentive to American patients who participate.

The loss of privacy and confidentiality is an additional risk. However, every reasonable effort will be made to limit breaches of privacy and confidentiality.

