**Data Analysis and Statistical Considerations**

Data from subjects who successfully complete the seven-day study will be used for analysis. The photos from Day 1 and Day 7 will be reviewed by the licensed physician using the Draize skin scoring system. Subjects will fill out a survey of their experiences of wearing the beeswax-pine resin adhesive. The 5-D itch scale will be used to quantify subjective experiences. All photos included in the dataset will be blinded before a licensed physician quantitatively indicate the level of skin irritation. Only the data of subjects who completed data collection for the entire 7-day duration will have their results quantified. Statistical tests will be completed on the results to draw conclusion about whether the beeswax-pine resin samples, in comparison to our control, caused skin irritation.

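### Subjects stopped early for a skin reaction are dropped from the irritation comparison, so an excess of reaction-related stops under the beeswax-pine rings would be understated

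*Protocol*

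**What the plan says.** Three parts of the Protocol act together.

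- **Stopping.** Data and Safety Monitoring names the effects in view: "Adverse side effects of the beeswax-pine resin mixture placed on the skin may include redness, rash, skin irritation, and infection". It then sets the rule: "Any signs of infection or other adverse side effects will result in the immediate cessation of the seven-day period for that subject". The sentence just before that rule is softer. For significant infection or irritation, the subject "will be evaluated by a licensed physician to evaluate whether they can continue in the study". Risk/Benefit Assessment adds a voluntary route for an uncomfortable reaction: "the subject may stop early, and the reaction will be noted".
- **Analysis set.** Data Analysis and Statistical Considerations limits the analysis to seven-day completers and then repeats the limit: "Only the data of subjects who completed data collection for the entire 7-day duration will have their results quantified".
- **Measurement.** Design and Procedures sets two photo times for Draize scoring: "Photo documentation with the dedicated camera will occur on Day 1 at the initial screening visit as noted above, as well as Day 7".

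The conclusion is judged against the definition in Purpose of the Study, where safe means "no greater external skin irritation or injury compared to standard commercially available ostomy appliance products".

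**The concern.** Redness, rash and irritation are both grounds for stopping and the outcome that the physician scores. A subject whose reaction is recognised before Day 7 is stopped, and the completer rule then removes that subject. Each subject wears two beeswax-pine rings and one control ring, so the whole matched set goes, whichever ring caused the reaction.

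Missingness is therefore tied to the outcome. The data most informative about harm are the most likely to be left out. If the beeswax-pine rings provoke more stops than the control, the bias favours the study's hypothesis that the mixture is safe. In a safety study that is the wrong direction for an error.

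This is not a detail left to a statistical analysis plan. The protocol itself fixes both the stopping rule and the analysis set, and a later plan could not readmit these subjects without contradicting it.

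**Working it through.** **Does anything return a stopped subject to the comparison?**

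- A reaction that is noted (Risk/Benefit Assessment) has no score and no place in the analysis.
- A subject stopped between Day 1 and Day 7 has no scheduled photo of the reaction to grade.
- Survey answers and the 5-D itch scale from a non-completer fall under the same completer rule.
- Recruitment is open-ended ("A minimum of 50 subjects will be recruited"), so stopped subjects might be replaced. That restores the count but not the reactions.

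An automatic stop, a stop after physician evaluation and a voluntary stop all meet the same exclusion. How Data and Safety Monitoring is read changes how many subjects are lost, not whether they are lost.

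**How large could the effect be?** The only figure in the protocol is N = 50 (Selection of Subjects/Inclusion-Exclusion Criteria). It gives no reaction rate, effect size or test, so there is no stated result to reproduce. Every count below is an assumption.

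Take one beeswax-pine ring against the control, with a reaction scored yes or no. Let T be the subjects reacting to the test ring only, C those reacting to the control only, and f the fraction of reactors stopped and dropped. The fraction f is assumed to be the same for both groups.

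- Completers: n = 50 − f(T + C)
- Difference among completers: (T − C)(1 − f) / n

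| T v C | All kept (f = 0) | Half dropped (f = 0.5) | All dropped (f = 1) |
|---|---|---|---|
| 5 v 1 | 4/50 = 8.0 points | 2/47 = 4.3 points (expected) | n = 44, 0 |
| 10 v 2 | 8/50 = 16.0 points | 5/44 − 1/44 = 4/44 = 9.1 points | n = 38, 0 |
| 20 v 4 | 16/50 = 32.0 points | 10/38 − 2/38 = 8/38 = 21.1 points | n = 26, 0 |

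Exact McNemar p-values from the discordant pairs:

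- 10 v 2: 2(1 + 12 + 66)/4096 = 158/4096 = 0.039
- 5 v 1: 2(1 + 6)/64 = 14/64 = 0.22

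So the 10 v 2 case goes from p = 0.039 to p = 0.22 when half are dropped. The 5 v 1 case already has p = 0.22 with everyone kept. The 20 v 4 case, halved to 10 v 2, still has p = 0.039.

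**Equal stopping.** With T = C = 4 and f = 0.5, n = 50 − 4 = 46 and each ring shows 2/46 = 4.3% instead of 4/50 = 8%. The difference stays at 0, but both rates are too low.

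**A second parametrisation.** Let reactions be independent within a subject, with probabilities pB (beeswax-pine) and pC (control), and let a share s of reactors be stopped. The completer difference is (pB − pC)(1 − s) / [(1 − s)(1 − q) + q], where q = (1 − pB)(1 − pC).

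- pB = 10%, pC = 2%: the true 8.0 points become 6.2, 4.3, 2.2 and 0 at s = 25%, 50%, 75% and 100%.
- pB = 20%, pC = 2%: the true 18 points become 14.3, 10.1, 5.4 and 0.

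The pattern is the same.

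**The case against.** Four points deserve weight.

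1. **Direction is conditional.** A reader might infer that any excess irritation under the beeswax-pine rings must be understated. The documents do not support that. The table assumes one stop fraction for both rings. With T = 10 and C = 2, if both control reactors stop and no test reactor does, completers show 10/48 v 0/48 = 20.8 points, above the true 16. That split may be less likely, but it is possible. This objection stands, and the claim is limited to the case where beeswax-pine causes more reaction-related stops.

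2. **Total erasure is the extreme.** A reader might also infer that the rule removes the whole difference. That needs every reactor to be recognised and stopped before Day 7. Design and Procedures refers severe reactions to a physician or dermatologist and, for other irritation, gives subjects a contact for reporting it. Some mild irritation would plausibly reach Day 7 and be scored. This also stands.

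3. **The test conclusion need not change.** It changes in the 10 v 2 example but not in the other two. The yes/no outcome and the McNemar test are illustrations; the protocol scores Draize and names no test.

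4. **Reactions are still recorded.** Daily surveys, the itch scale and the noted reaction would document them, so it would be wrong to say that they vanish from the safety record. They are absent only from the comparison that decides whether the mixture is safe.

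None of these removes the exclusion of stopped subjects or its dependence on the outcome.

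**Conclusion.** The point holds in conditional form. Followed as written, the protocol excludes subjects because of the outcome it compares. If beeswax-pine rings cause more reaction-related stops than the control, their excess irritation is understated and the result is pushed toward safe. If stops are equal, the comparison is unbiased but each ring's irritation rate is understated.

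The size cannot be fixed from the document: no reaction rate is given, and Risk/Benefit Assessment considers a reaction unlikely. Under the assumed counts and a common stop fraction, true differences of 8, 16 and 32 points fall to 4.3, 9.1 and 21.1 points when half of the reactors are dropped. They reach 0 only at the extreme.

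The tension between the two adjacent stopping sentences in Data and Safety Monitoring is a separate, minor drafting point that concerns significant reactions only. The argument here does not need it.

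**What to change.** Keep the immediate stop. For reaction-related stops, replace the completer-only rule in Data Analysis and Statistical Considerations as follows.

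1. Record the day, the reason and the responsible ring for each stop.
2. Where possible, photograph all three sites at the stop with the existing camera and mask the automatic date stamp so that grading stays blinded. Use the Draize score for each ring in place of Day 7.
3. Where no stop photo exists, assign the responsible ring the worst Draize rank. This states how a stop enters an ordinal outcome.
4. Report reaction-related stops by ring as a separate outcome.
5. If the responsible ring cannot be identified, including a possible reaction to the Tegaderm covering all three, give two sensitivity analyses. One assigns the stop to the beeswax-pine rings and the other to no ring.

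If the two stopping sentences are also tidied, state that the rings come off at once for any reaction and that the physician then evaluates the significant ones.

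The cost is a short amendment, a few extra data fields and one unscheduled photo per stopped subject, using the existing grader. No subjects are added. The downside is that attributing a stop to a ring is partly subjective.

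### Subjects stopped early for a skin reaction are left out of the comparison that decides whether the mixture is safe

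*Protocol*

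**What the plan says.** Purpose of the Study defines safe by comparison: external skin irritation or injury must be no greater than with a standard commercial product such as the barrier ring used as control. Each subject wears three rings: two beeswax-pine samples and the control.

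Data and Safety Monitoring lists the expected harms: "Adverse side effects of the beeswax-pine resin mixture placed on the skin may include redness, rash, skin irritation, and infection". It then sets the stopping rule: "Any signs of infection or other adverse side effects will result in the immediate cessation of the seven-day period for that subject". The sentence just before gives a different route: "Any significant infection or irritation of the skin that causes serious concern for the subject will be evaluated by a licensed physician". Under that sentence, whether the subject goes on is the physician's decision. Risk/Benefit Assessment adds a third threshold. There a subject may stop if the reaction is too uncomfortable to bear for the full week, and the reaction is noted.

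Data Analysis and Statistical Considerations limits the analysis twice: "Data from subjects who successfully complete the seven-day study will be used for analysis", and "Only the data of subjects who completed data collection for the entire 7-day duration will have their results quantified". Photographs are planned for Day 1 and Day 7 only. A physician grades them blinded, "indicating the appropriate level of skin irritation and rash by utilizing the Draize skin scoring system".

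**The concern.** The event that ends participation is the event the study exists to count. Skin irritation and rash are two of the four harms named in the stopping section, and the Draize grading is described as scoring exactly these. A reaction found during the week triggers a stop, the stop makes the subject a non-completer, and non-completers are not quantified. Exclusion therefore depends on the outcome, and better detection removes more reactors.

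Safety is the study's only objective. If beeswax-pine irritates more often than the control, the completers-only comparison understates the excess and could support a conclusion of safe that the full set of treated subjects would not.

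**Working it through.** **Step 1: follow one subject through the text.** A subject shows redness under a beeswax-pine ring on Day 3 and reports it.
- Data and Safety Monitoring: redness is a named adverse side effect, so the seven-day period ends at once.
- Data Analysis: the subject did not complete seven days, so no results are quantified, including those for the control and the other beeswax-pine ring.
- Design and Procedures: no graded photograph is planned between Day 1 and Day 7, so no Draize score is scheduled at the stop.
- Risk/Benefit Assessment: the reaction is noted. No section says how the note enters the comparison by ring type.

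A subject whose reaction is first seen at Day 7 has completed and stays in.

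**Step 2: size.** The protocol gives 50 subjects and no reaction rates, so there is no figure to reproduce. The rates below are assumptions.

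Inputs: *p_t* and *p_c* are the true proportions reacting under beeswax-pine (treated as one site for simplicity) and under control. *d* is the share of reactors detected and stopped before Day 7. Sites are taken as independent.

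- Reaction rate among completers = p(1 − d) / (1 − pd)
- Expected completers = 50 × (1 − p_t·d) × (1 − p_c·d)

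Worked case, 20% against 5% with d = 0.5:
- Beeswax-pine: 0.20 × 0.5 / (1 − 0.10) = 0.10 / 0.90 = 11.1%
- Control: 0.05 × 0.5 / (1 − 0.025) = 0.025 / 0.975 = 2.6%
- Difference: about 8.5 points instead of 15
- Completers: 50 × 0.90 × 0.975 = 43.9

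Difference among completers, in percentage points, over a range of assumptions:

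| True rates (beeswax-pine vs control) | True difference | d = 25% | d = 50% | d = 75% | d = 100% |
|---|---|---|---|---|---|
| 5% vs 2% | 3 | 2.3 | 1.6 | 0.8 | 0 |
| 10% vs 2% | 8 | 6.2 | 4.3 | 2.2 | 0 |
| 20% vs 5% | 15 | 12.0 | 8.5 | 4.6 | 0 |
| 30% vs 5% | 25 | 20.5 | 15.1 | 8.4 | 0 |

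**Step 3: direction.** If *p_t* = *p_c*, both rates fall equally and the difference stays 0. The bias towards safe arises when reactions are more frequent under beeswax-pine.

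**Step 4: effect of the stopping threshold.** The three thresholds (any sign; a physician's decision when the subject is seriously concerned; too uncomfortable to continue) correspond to different values of *d*. The first gives the largest. The other two move the result towards the left of the table, but *d* is above zero whenever anyone stops for a reaction.

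**Step 5: after the change.** Counting each early-stopped reaction at its site over all treated subjects brings the difference back to about 15 points in the worked case. What cannot be recovered is a reaction at another site that would have appeared after the stop. With independent sites, at most 0.20 × 0.05 = 1% of subjects would react at both.

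**The case against.** The strongest defence has four parts.

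- *The reaction is recorded.* This stands: the event is not lost from the records. It is lost from the quantified comparison, which is what decides safety.
- *Any sign may not be the operative threshold.* If physician discretion or discomfort governs, milder reactors continue and are graded at Day 7. This stands and limits the size. It does not remove the problem, because those who do stop remain unquantified.
- *A stop removes the control site too.* This also stands: the comparison is distorted only when reactions differ in frequency between rings.
- *An analysis plan could handle it.* This does not stand. The protocol itself fixes the completers-only rule, in two sentences.

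Two stronger readings are tempting and should be resisted. A reader might infer that the daily survey never asks about the skin, because it is described only by "subjects will be provided a survey at the end of each day to assess their overall well-being" and space for concerns. The survey is not shown. Other sections mention the 5-D itch scale, subjects expose all three sites daily, and they have a contact for reporting any skin irritation. A reader might also infer that a reaction short of severe reaches a physician only if it worries the subject. One sentence says so, but the next stops the subject at any sign whatever the level of concern, which is the more protective instruction. What remains is a conflict of wording.

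**Conclusion.** The point holds. As written, stopping for a reaction combined with a completers-only analysis removes outcome events from the safety comparison. It biases that comparison towards safe when beeswax-pine reacts more often than the control.

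The size cannot be fixed from the protocol. It rests on the assumed true rates, the share of reactors stopped before Day 7 and independence between sites. A reader might infer that the comparison would contain no reactions at all. That is only the extreme in which every reactor is detected and stopped early, and the protocol does not show that this would happen. A partial loss is the safer reading.

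The conflict between the stopping thresholds is a lesser, related defect: staff cannot apply all three to the same subject, and the choice between them changes how many reactors are lost.

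**What to change.** 1. Amend Data Analysis and Statistical Considerations so that every skin reaction, including in subjects stopped early, counts as an irritation event for the ring site where it occurred. Compare these events by ring type over all subjects who had rings applied. Keep the Day 7 Draize comparison in completers beside it as secondary or supportive.
2. Replace the conflicting sentences in Data and Safety Monitoring and Risk/Benefit Assessment with one stopping and referral rule triggered by the reported sign. It should say which signs stop the subject at once and which a physician may allow to continue. The clinical threshold is for the sponsor and physician to set.

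The cost is text changes in three sections and recording the ring site with each noted reaction; no new scheduled visits are needed. The downside is that early-stop reactions may have no blinded Draize grade, so the all-treated comparison has to use a coarser yes/no reaction by site, partly from unblinded reports. A photograph at the early stop would help but would mean an unscheduled visit, and the fix does not depend on it.

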**Privacy, Data Storage & Confidentiality**

Any data that is stored in paper or non-digital format will be locked in a file cabinet within a key-accessed office. The office will be locked when not in use by the study team. Picture data stored via camera will be stored in a portable lock box when transportation is needed. However, picture data will be deleted as soon as possible after data is transferred to a secure server. Any data that is stored in electronic format will be housed on a secure server behind the Duke University Medical Center firewall and/or REDCap. Any personnel involved with data collection will be trained on the study's Secure Data Collection SOP.

